4.3.2.2 Fenebrutinib and Placebo Compliance

The following measures will be taken to assess patient compliance with study drug. For Cohort 1, patients will be directed to bring the study drug bottle to each visit after randomization. In addition, sites will be responsible for prepopulating the dates on the dosing label (affixed to the bottle) for when patients are scheduled to take study drug. The patients will record the times (a.m. or p.m.) that they take each dose in their eDiary. The number of tablets issued minus the number of tablets returned will be used to calculate the number of tablets taken and compliance.

For Cohort 2, sites will be responsible for prepopulating the dates on the blister wallets for when patients are scheduled to take study drug. The patients will record the times (a.m. or p.m.) that they take each dose in their eDiary. Patients will be instructed to return all blister wallets (used and unused) at each study visit for assessment of compliance and for medication disposal.

Compliance will be documented on the source record. Any overdose or incorrect administration of study drug should be noted on the Study Drug Administration electronic

Case Report Form (eCRF). Adverse events associated with an overdose or incorrect administration of study drug should be recorded on the Adverse Event eCRF. If compliance is $\leq 80\%$, the investigator or designee is to counsel the patient and ensure steps are taken to improve compliance.

4.3.2.3 *Background Therapy: Standard-of-Care H1 Antihistamines for CSU*

The following H1 antihistamine medications are allowed:

- *Cetirizine 10–40 mg QD*
- *Levocetirizine 5–20 mg QD*
- *Fexofenadine 180–720 mg QD*
- *Loratadine 10–40 mg QD*
- *Desloratadine 5–20 mg QD*
- *Rupatadine 10–40 mg QD*
- *Bilastine 20–80 mg QD*

All patients will be allowed to take study-defined, second-generation, H1 antihistamine medications consistent with standard-of-care (i.e., up to 4 times the approved dose per local treatment guidelines) during the screening, treatment, and follow-up periods. Patients should remain on a stable H1 antihistamine regimen throughout the study period. Loratadine (10 mg) or cetirizine (10 mg) will be provided and used on an as-needed basis (maximum 1 per day) during screening, treatment, and follow-up periods). Therapies used for the treatment of CSU prior to enrollment will be collected as part of the patient’s medical history.

Patients taking either LTRAs or H2 blockers for diseases other than CSU (e.g., asthma or gastroesophageal reflux disease, respectively) at screening will be permitted to continue their use at a stable dose during the study. These diseases must be recorded as part of the medical history collected during the screening period. Inhaled asthma controllers, including inhaled corticosteroids, are permitted during the study.

4.3.3 Investigational Medicinal Product Accountability

All IMPs required for completion of this study (fenebrutinib and placebo) will be provided by the Sponsor where required by local health authority regulations. The study site will acknowledge receipt of IMPs using the IxRS to confirm the shipment condition and content. Any damaged shipments will be replaced.

IMP either will be disposed of at the study site according to the study site’s institutional standard operating procedure or will be returned to the Sponsor with the appropriate documentation. The site’s method of IMP destruction must be agreed to by the Sponsor. The site must obtain written authorization from the Sponsor before any IMP is destroyed, and IMP destruction must be documented on the appropriate form.

Accurate records of all IMPs received at, dispensed from, returned to, and disposed of by the study site should be recorded on the Drug Inventory Log.

4.3.4 Post-Trial Access to Fenebrutinib

Patients may be eligible to receive fenebrutinib as part of open-label extension study (GS40868) offered by the Sponsor (Genentech, a member of the Roche Group), as described in Section 3.1.2. The Roche Global Policy on Continued Access to Investigational Medicinal Product is available at the following website:

http://www.roche.com/policy_continued_access_to_investigational_medicines.pdf

4.4 CONCOMITANT THERAPY AND ADDITIONAL RESTRICTIONS

Concomitant therapy includes any medication (e.g., prescription drugs, over-the-counter drugs, vaccines, herbal or homeopathic remedies, nutritional supplements) used by a patient from 14 days prior to initiation of study drug to the study completion/ discontinuation visit. All such medications (*including standard-of-care H1 antihistamines for CSU*) should be reported to the investigator and recorded on the Concomitant Medications eCRF.

4.4.1 Permitted Therapy

Patients who use oral contraceptives, hormone-replacement therapy, or other maintenance therapy should continue their use. All concomitant medications should be reported to the investigator and recorded on the appropriate eCRF. Patients will be encouraged to use the minimal dose required to control their symptoms.

For the purposes of this study, dietary supplements are defined as vitamins, minerals, purified food substances, and herbals with pharmaceutical properties.

Vitamins, minerals, and purified food substances are allowed in amounts not known to be associated with adverse effects (e.g., hypervitaminosis). Herbals with pharmaceutical properties are allowed only if there is acceptable evidence of no CYP3A inhibition or induction (refer to Section 4.4.3 for a list of prohibited concomitant medications, including herbal products). Otherwise, herbals with pharmaceutical properties must be discontinued for at least 4 weeks prior to the first dose of study medication, unless there are sufficient data available regarding the duration of an herbal medication's PK and PD effects to allow a shorter washout to be specified (e.g., 5 half-lives). Please direct any questions to the Medical Monitor.

4.4.2 Cautionary Therapy

4.4.2.1 Acid-Reducing Agents

Patients who use antacids (e.g., Pepto-Bismol[®], Rolaid[®]) for symptomatic relief of heartburn should take fenebrutinib or matching placebo at least 2 hours before or 2 hours after antacid administration because gastric acid improves fenebrutinib absorption.

Patients may be treated with PPIs or H2RAs at up to the maximum recommended dose according to local labeling. The dose should remain stable for at least the 2 weeks before randomization and throughout the study.

At visits with scheduled PK assessments (see [Appendix 1](#)), any use of PPIs, H2RAs, and/or other antacids (e.g., Pepto-Bismol[®], Roloids[®]) should be recorded as concomitant medications, including the date and time of last administration.

4.4.2.2 *Statins*

Several lipid-lowering agents (statins) are metabolized by CYP3A (simvastatin, lovastatin) and/or transported by BCRP (rosuvastatin, atorvastatin), and thus may be affected by drug-drug interaction with fenebrutinib, therefore, dose adjustments of these medications should be considered (Kellick et al. 2014).

- *Simvastatin: recommended maximum dose of 10 mg/day*
- *Lovastatin: recommended maximum dose of 20 mg/day*
- *Rosuvastatin: recommended maximum dose of 10 mg/day*
- *Atorvastatin: recommended maximum dose of 20 mg/day*

The use of statins has been associated with myopathy, which can manifest as weakness, tenderness or muscle pain with elevations of creatine kinase (CK) above ten times the ULN. In severe cases, myopathy can cause rhabdomyolysis with or without acute kidney injury secondary to myoglobinuria, and rare fatalities due to rhabdomyolysis have occurred. The risk of myopathy is increased by elevated plasma levels of statins. Predisposing factors for myopathy include advanced age (≥ 65 years), female gender, uncontrolled hypothyroidism, renal impairment, or the use of concomitant medications that increase the plasma levels of the statin.

4.4.2.3 CYP3A and BCRP-Mediated Drug Interactions

Preliminary data from a clinical drug-drug interaction study (Study GP39616) suggest that fenebrutinib can be classified as a mild inhibitor of CYP3A at clinically relevant doses. It is possible that fenebrutinib inhibition of CYP3A may alter the metabolism of CYP3A substrates and result in increased plasma concentrations of CYP3A substrates. Therefore, medications in the following categories (listed in detail in [Appendix 5](#)) should be used with caution in consultation with the Medical Monitor (or delegate) as necessary unless otherwise specified in [Appendix 5](#):

- Sensitive CYP3A substrates
- CYP3A substrates with a narrow therapeutic window

The use of hormone-replacement therapy or hormonal contraceptives containing the CYP3A substrate ethinylestradiol (with the concomitant use of a barrier method) is permitted; however, these agents should be used with caution, and patients should be counseled regarding the potential risks and benefit of these medications per the local prescribing information. *Ethinyl estradiol is metabolized by CYP3A so plasma*

concentrations of ethinyl estradiol are expected to increase in the presence of fenebrutinib (Zhang et al. 2007, Wang et al. 2004). Ethinyl estradiol is not a sensitive substrate of CYP3A (Drug Development and Drug Interactions: Table of Substrates, Inhibitors and Inducers, www.fda.gov). Therefore, the magnitude of increase in ethinyl estradiol plasma concentrations is expected to be less than the increase observed in midazolam concentrations (i.e., less than 2-fold) in Study GP39616, a drug-drug interaction study evaluating the effect of fenebrutinib on the PK of the sensitive CYP3A substrate midazolam. Minor increases in ethinyl estradiol concentrations are not generally associated with adverse events (e.g., Ortho Tri-Cyclen® USPI). Ethinyl estradiol efficacy is expected to be maintained, and ethinyl estradiol continues to be considered a reliable and effective form of contraception in combination with fenebrutinib.

Preliminary data from Study GP39616 also suggest that fenebrutinib can be classified as a moderately sensitive substrate of CYP3A at clinically relevant doses. There is a moderate potential for a drug-drug interaction with any medication that strongly inhibits or induces this enzyme. Therefore, medications in the following categories (listed in detail in [Appendix 5](#)) should be avoided for 7 days or 5 half-lives, whichever is longer, prior to the first dose of study drug and until the last dose of study drug. If use of one of these medications is necessary, the risks and benefits should be discussed with the Medical Monitor (or delegate) prior to concomitant administration with study drug:

- Strong CYP3A inhibitors
- Moderate or strong CYP3A inducers

Lastly, preliminary data from Study GP39616 suggest that fenebrutinib is a moderate inhibitor of the breast cancer resistance protein (BCRP) (also known as ABCG2) transporter protein at clinically relevant doses. There is a potential for increased plasma concentrations of drugs that are known to be substrates of the BCRP transporter. Plasma concentrations of the medications in the following category (listed in detail in [Appendix 5](#)) may increase; therefore, they should be used with caution in consultation with the Medical Monitor (or delegate) as necessary unless otherwise specified in [Section 4.4.1](#).

The medications listed above and in [Section 4.4.1](#) are not necessarily comprehensive. Thus, the investigator should consult the prescribing information for any concomitant medication as well as the Internet references provided below when determining whether a certain medication is metabolized by or strongly inhibits or induces CYP3A. The investigator should contact the Medical Monitor if questions arise regarding medications not listed above.

<https://www.fda.gov/Drugs/DevelopmentApprovalProcess/DevelopmentResources/DrugInteractionsLabeling/ucm093664.htm> (Tables 3-1, 3-2, 3-3, and 5-1)

<http://medicine.iupui.edu/clinpharm/ddis/table.aspx>

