Appendix 5 Concomitant Medications (Including Foods and Herbal Products)

| Class | Expected Interaction | Recommendation | Examples of Drugs in this Class ^a |
|--|--|--|---|
| Antacids | Decreased fenebrutinib absorption due to increased gastric pH | Take fenebrutinib 2 hours before or 2 hours after antacid | 
 • Pepto-Bismol, Roloids |
| Moderate or strong CYP3A inhibitors | Increased fenebrutinib plasma concentrations due to inhibition of metabolism | Avoid for 7 days or 5 half-lives (whichever is longer) prior to first dose of study drug and during the treatment period | 
 • Antimicrobials (clarithromycin, erythromycin, itraconazole, ketoconazole, telithromycin, troleandomycin, voriconazole, posaconazole) • Antidepressants (nefazodone) • Antihypertensive/cardiac (verapamil, diltiazem) • Other (grapefruit juice, Seville orange juice, pomegranate, star fruit) |
| CYP3A inducers | Decreased fenebrutinib plasma concentrations due to increased metabolism | Avoid for 7 days or 5 half-lives (whichever is longer) prior to first dose of study drug and during the treatment period | 
 • Antimicrobials (rifampin, rifapentine, rifabutin) • Antidepressants (St. John's wort, hyperforin) • Antiepileptics (carbamazepine, phenytoin, phenobarbital, hyperforin) • Diabetes (pioglitazone, troglitazone) • Other (modafinil, bosentan) |

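### Section 4.4.2.3 avoids only strong CYP3A inhibitors while the current Appendix 5 avoids moderate or strong ones, so sites get opposite answers for an unlisted moderate inhibitor

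*Combined protocol and SAP*

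**What the plan says.** Section 4.4.2.3 treats fenebrutinib as a moderately sensitive CYP3A substrate and draws three rules from that, each limited to strong inhibitors:

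- Rationale: "There is a moderate potential for a drug-drug interaction with any medication that strongly inhibits or induces this enzyme".
- Avoid list: the inhibitor bullet reads "Strong CYP3A inhibitors", while the inducer bullet beside it covers both moderate and strong inducers. Listed drugs "should be avoided for 7 days or 5 half-lives, whichever is longer, prior to the first dose of study drug" and until the last dose. If one is needed, "the risks and benefits should be discussed with the Medical Monitor (or delegate) prior to concomitant administration with study drug".
- Look-up rule: the lists are said not to be comprehensive, so investigators consult prescribing information and web tables "when determining whether a certain medication is metabolized by or strongly inhibits or induces CYP3A". Beyond that, "The investigator should contact the Medical Monitor if questions arise regarding medications not listed above".

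Appendix 5, cited in the same section for the detail of the avoid categories, has a CYP3A inhibitor row whose class label begins "Moderate or strong". Its recommendation is to avoid, over the same pre-dose window and through the treatment period. The strength label and the verapamil/diltiazem entry are in italics. The amendment summary says that italics mark substantive new information.

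**The concern.** The amendment widened the appendix but left the body text at the narrower limit. The sponsor's reason for the wider limit stands in the appendix row itself: higher fenebrutinib plasma concentrations. Section 1.2.3 likewise says that CYP3A inhibitors may raise fenebrutinib levels, and sets no strength threshold. The next bullet in Section 4.4.2.3 shows that the section separates strengths when it means to, so the strong-only wording looks like text missed in the update.

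At stake is consistent handling of concomitant medication and one safety step. The discussion with the Medical Monitor before co-administration is written only in Section 4.4.2.3 and attaches to its listed categories. The Appendix 5 inhibitor row says avoid and does not repeat the step. A site that works from the body text could start a moderate inhibitor without it.

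**Working it through.** This is a comparison of texts; no formula applies. The plan gives no figure to reproduce, and the documents give no fold-change in fenebrutinib exposure for a moderate inhibitor.

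**1. The same instruction in two places**

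| Element | Section 4.4.2.3 | Appendix 5 |
|---|---|---|
| Inhibitor class | "Strong CYP3A inhibitors" | "Moderate or strong" |
| Window | 7 days or 5 half-lives, the longer, to last dose | Same pre-dose window, and during treatment |
| Unlisted drugs | Look up whether the drug strongly inhibits | Class label governs; the drugs are examples; the footnote sends sites to web tables with no strength limit |
| Medical Monitor | Discuss risk and benefit before use of a listed category; contact if questions arise | Consult if necessary |

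**2. Counts.** Section 4.4.2.3 has three strong-only wordings (one bullet, two sentences) against one wider row in Appendix 5. That row names 8 antimicrobials + 1 antidepressant + 2 antihypertensive/cardiac drugs = 11 drugs, plus 4 foods. Two of the 11 drugs, verapamil and diltiazem, are new in italics.

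**3. Which drugs get different answers**

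- A strong inhibitor, named or not: avoided under both texts.
- A drug named in the Appendix 5 row: avoided, because Section 4.4.2.3 sends the reader there.
- A moderate inhibitor not named: avoided under the Appendix 5 class label, but cleared by the Section 4.4.2.3 look-up rule. This is where the texts conflict.

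**4. What other rules already catch**

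- Antimicrobials: Table 5 withholds study treatment during antimicrobial therapy for self-limited infections, and discontinues it for serious or opportunistic infections or those needing IV agents. Section 4.1.2 excludes patients given oral antimicrobials in the 2 weeks before screening or during it.
- Herbals: Section 4.4.1 allows those with pharmaceutical properties only with acceptable evidence that they neither inhibit nor induce CYP3A.
- Foods: Section 4.4.4 prohibits the furanocoumarin-containing items.

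What remains is mainly unlisted moderate inhibitors outside these three groups.

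**5. Safety backstop.** Chemistry, including ALT and AST, is scheduled on Days 1, 8, 15, 29 and 57. Table 5 withholds treatment at AST or ALT 3.0–5.0 × ULN. Day 43 is a phone call, so there is no scheduled chemistry for 57 − 29 = 28 days.

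**6. Cross-references.** Section 4.4.2.3 points twice to Section 4.4.1. The reference beside the look-up rule treats Section 4.4.1 as a drug list for CYP3A interactions, which it is not. The other sits in the BCRP sentence. The parallel sentence on CYP3A substrates, "in consultation with the Medical Monitor (or delegate) as necessary unless otherwise specified in", ends by naming Appendix 5.

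**The case against.** The best defence is that Appendix 5 is built by class. Its row label defines the class, the last column gives examples, and Section 4.4.2.3 itself sends the reader there for the avoid categories. A site that follows the reference would avoid an unlisted moderate inhibitor. That stands. A reader might infer that the protocol leaves every moderate inhibitor outside the 11 named drugs uncovered; the class label shows that it does not. The defence does not remove the conflict, because the look-up rule in the body gives the opposite answer and no text says which prevails.

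A second defence is that the antimicrobial, herbal and food rules take away much of the practical exposure. That also stands, and it limits the size of the point. So does the fact that this is cautionary therapy, where use remains possible after discussion, and not an absolute prohibition.

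A third concerns the cross-references. It is tempting to call both Section 4.4.1 references wrong. Section 4.4.1 does let oral contraceptives and hormone-replacement therapy continue, so the reference in the BCRP sentence could be an intended exception. Only the one beside the look-up rule is clearly wrong.

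**Conclusion.** The inconsistency is real, lies in current text and should be corrected. Three wordings in Section 4.4.2.3 stop at strong inhibitors where the sponsor's current appendix does not. An investigator who applied the look-up rule as written would clear a drug that the appendix says to avoid, without the required discussion. The practical reach is modest, for the reasons in the working.

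This rests on reading the italicised appendix row as the sponsor's present intention, which the amendment summary's convention supports, and on finding no precedence rule.

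A reader might go further and infer raised exposure, liver harm or a distorted treatment comparison. The documents do not support that. They give no fold-change for moderate inhibitors and no expected frequency of use. The transaminase elevations reported in the randomised studies of autoimmune indications were still blinded to treatment. No effect on power or on the between-arm comparison is claimed.

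**What to change.** In Section 4.4.2.3:

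1. Change the bullet to *Moderate or strong CYP3A inhibitors*.
2. In the rationale and look-up sentences, use *moderately or strongly inhibits or induces*. Applying the qualifier to both verbs keeps the sentences in line with the existing inducer bullet.
3. In the sentence introducing the look-up rule, replace the Section 4.4.1 reference with Appendix 5.
4. Check whether the Section 4.4.1 reference in the BCRP sentence should also read Appendix 5; keep it if an exception is intended.

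Leave the Appendix 5 inducer row as it is. It carries no strength limit and is the stricter text.

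The cost is four wording edits (one bullet, two sentences, one cross-reference) and one check, with no new procedure. Sites that relied on Section 4.4.2.3 alone would face slightly tighter concomitant-medication limits, which the sponsor has already adopted in the appendix.

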4.4.3 Prohibited Therapy

Prior to the screening visit (Day -14 for both cohorts) as specified below, and during the study (not including the safety follow-up period if patient failed additional H1 antihistamine for worsened symptoms; see Section 3.1) the following medications and treatments will be restricted. Patients who receive these medications as therapy for CSU will be discontinued from the study treatment but will be followed for safety evaluation:

- Systemic or topical corticosteroids (prescription or over the counter), hydroxychloroquine, methotrexate, cyclosporine, or cyclophosphamide within 30 days prior to screening if used routinely (daily or every other day during 5 or more consecutive days) – *The use of corticosteroids may be used for exacerbations*
- Doxepin within 30 days prior to screening
- Omalizumab or other monoclonal antibody therapies used to treat CSU within 4 months prior to screening
- IVIG within 30 days prior to screening
- Plasmapheresis within 30 days prior to screening
- LTRAs within 1 day prior to screening
- Astemizole, terfenadine, and ebastine within 1 day prior to screening

4.4.3.1 Live or Attenuated Vaccinations

Immunization with a live or attenuated vaccine is prohibited within 6 weeks prior to study drug administration on Day 1 and for the duration of study participation, including the 4-week safety follow-up period after the administration of the last dose. See Section 5 for further details and precautions around vaccinations.

4.4.4 Prohibited Food

Use of the following foods is prohibited during the study and for at least 7 days prior to initiation of study treatment: furanocoumarin derivatives as found in grapefruit, Seville orange, pomegranate, or star fruit juice or products. Please refer to [Appendix 5](#) for additional information.

4.4.5 Additional Restrictions

Patients in both cohorts should be fasting overnight for >8 hours prior to the PK draw and/or fasting lipid panel on Days 1, 8, 29, 57, and 85 (see [Appendix 1](#)).

4.5 STUDY ASSESSMENTS

Please see [Appendix 1](#) for the schedule of activities to be performed during the study.

